## **PROTOCOL TITLE**

A Clinical Trial of a Hemp-Derived Cannabidiol Product for Anxiety

## **FUNDING**

Sponsored by Charlotte's Web (formerly known as Stanley Brothers Bio Tec)

## **VERSION DATE**

5/12/2023

## **SPECIFIC AIMS**

Concisely state the objectives of the study and the hypothesis being tested.

The proposed investigation is designed to examine the impact of 6 weeks of treatment with a sublingual high-cannabidiol industrial hemp-derived compound on individuals with symptoms of anxiety.

**Specific Aim 1:** To assess pre- and post-hemp treatment clinical state ratings of anxiety and quality-of-life ratings in individuals with symptoms of anxiety.

**Specific Aim 2:** To assess pre- and post-hemp treatment performance on a range of neurocognitive measures designed to examine cognitive function.

**Specific Aim 3:** In a subset of individuals, to examine structural and functional changes that may occur in the brain following treatment with a high-CBD hemp product using multimodal magnetic resonance imaging (MRI) techniques.

## **BACKGROUND AND SIGNIFICANCE**

Provide a brief paragraph summarizing prior experience important for understanding the proposed study and procedures.

*Cannabis sativa* has been used medicinally for a range of disorders for thousands of years, including anxiety. Cannabis is comprised of more than 100 cannabinoids; D-tetrahydrocannabinol (Δ9-THC) is the major psychoactive constituent, and cannabidiol (CBD) is the major non-psychoactive constituent that has been touted to have a variety of potential medicinal benefits. Industrial hemp is a variety of the *Cannabis sativa* plant, which until recently was grown specifically for industrial uses, such as textiles. Hemp has much lower concentrations of THC than cannabis, defined as THC<0.3% by weight. In recent years, some hemp strains have been bred to produce particularly high concentrations of CBD with very low concentrations of THC, virtually eliminating the potential for intoxicating effects. Extracts from these hemp strains are manufactured into a variety of oils, capsules, sprays, etc., available in brick-and-mortar stores across the country as well as on the Internet.

Previous studies have demonstrated CBD's acute anxiolytic potential in both animals and humans. Recently, our group began the first ever clinical trial of a high-CBD compound for anxiety. This trial, studied under IND [REDACTED], examines the impact of a high-CBD, low-THC cannabis-derived sublingual solution on measures of anxiety, mood, quality of life, and cognition over a 4-week treatment period. Interim analyses completed on the first 5 subjects who completed the trial were extremely compelling; analyses indicate that patients reported a 68.29% reduction in anxiety symptoms on the primary outcome measure, the Beck Anxiety Inventory (BAI), from the baseline to final visit. The study product is very well-tolerated, with no serious adverse events occurring to date.

The proposed investigation will be the first of its kind to conduct a clinical trial of an industrial hemp-derived product in individuals with anxiety. Despite the recent interest in MC and cannabinoid-based products, the availability of hemp-derived products in all 50 states, and anecdotal evidence suggesting that hemp-derived products may have a profound anxiolytic effect, no studies have conducted a clinical trial of a hemp-derived product in individuals who suffer from anxiety. Further, none have systematically evaluated baseline and follow-up clinical state and related quality of life measures in individuals taking hemp-derived products, or assessed measures of cognition, brain structure and function before and after treatment using neuropsychological measures and neuroimaging. The recent passage of the Farm Bill of 2018 has resulted in the exclusion of industrial hemp-derived products (THC content <0.3% by weight) from the Controlled Substances Act (CSA). As such, it is now possible to conduct clinical trials on industrial hemp-derived CBD products, including those such as Charlotte's Web (CW), which many thousands of consumers have purchased in recent years. As such, we will assess a proprietary hemp-derived formulation manufactured by CW [REDACTED]

[REDACTED]; the custom formulation contains approximately 30mg/ml of CBD and 0.8 mg/ml THC. In addition to providing information regarding the potential efficacy of an industrial hemp-derived CBD product for anxiety, this study will allow the comparison of a NIDA-based product, studied in our other IND and which lacks ecological validity, to a product that many thousands of consumers have used.

## RESEARCH DESIGN AND METHODS

Briefly describe study design and anticipated enrollment, i.e., number of subjects to be enrolled by researchers study-wide and by Partners researchers. Provide a brief summary of the eligibility criteria (for example, age range, gender, medical condition). Include any local site restrictions, for example, "Enrollment at Partners will be limited to adults although the sponsor's protocol is open to both children and adults."

This study is an investigation of 40 subjects who have expressed interest in using CBD for anxiety. Subjects will complete study visits at McLean Hospital. Following a preliminary phone screen and prior to any evaluation, all study subjects will be required to sign a McLean Hospital approved informed consent form that describes all study procedures. The phone screen includes questions related to medical history, substance use history, demographics, and screening questions from the OASIS (see below) to determine whether the subject has anxiety.

Individuals will be assessed at baseline and throughout 6 weeks of treatment with compounds administered as sublingual tinctures in a double-blind, randomized procedure: subjects will receive either a high CBD product or matched placebo. Each product will be analyzed and verified at an

outside lab for safety and potency. Subjects will self-administer 0.5 ml (15mg/ml) of CBD or placebo sublingually two times daily. At each weekly visit, individuals will complete clinical scales and have a check-in with study staff. Neuropsychological testing will be performed at baseline and the final visit in order to assess cognitive performance. Buccal swabs will be collected for DNA analysis from all participants in the double-blind phase. Finally, a subset of individuals will receive an hour-long MRI scan at baseline and the final visit, with both resting state and task-related functional magnetic resonance imaging (fMRI) in each MRI session. In addition, a brief diffusion tensor imaging (DTI) sequence will also be acquired to examine white matter fiber tract integrity, and magnetic resonance spectroscopy (MRS) will be conducted to examine levels of certain metabolites in the brain. Subjects will complete study drug diaries manually (pencil and paper) or electronically.

In order to assess the efficacy of the dose chosen for the double-blind study, we will also conduct a small open-label trial of the CBD solution prior to initiating the double-blind study. This open-label trial will enroll up to 12 participants who are interested in using CBD, and who have anxiety. This trial will determine whether patients derive clinical benefits at the current dosage proposed for the active treatment arm of the double-blind trial. This trial will examine all components of the originally proposed study.

Subjects will be recruited through IRB-approved advertisements and flyers in regions that have approved medical marijuana. Additionally, medical marijuana healthcare facilities throughout New England, including CannaCare, Integr8, MMJ Physician Practice, and others, may also refer interested patients to contact the study recruitment line for further screening. These healthcare groups provide their interested patients who meet for general inclusion criteria with study recruitment materials. The total sample size for the double-blind study is 40 (20 CBD, and 20 placebo); up to 15 of each group (30 total) will also complete the MRI scanning protocol. For the open-label trial, the total sample size is 12.

Inclusion Criteria:

- 1) Subject has provided informed consent
- 2) Subject is 18 or older
- 3) Subject is a native English speaker or acquired English prior to age 5
- 4) Subject scores a minimum of 16 on the Beck Anxiety Inventory (BAI) OR a minimum of 8 on the Overall Anxiety Severity and Impairment Scale (OASIS) at the screening visit

Exclusion Criteria:

Subjects will be excluded if they report any of the following:

- 1) Non-native English speakers
- 2) Estimated IQ < 75
- 3) Meets criteria for DSM-IV classification of current substance abuse/dependence, psychotic disorder, bipolar disorder, or an eating disorder
- 4) A first-degree relative with a psychotic disorder
- 5) A history of head injury or loss of consciousness greater than 5 minutes
- 6) Currently uses marijuana or cannabinoid-based products more frequently than 1x/month
- 7) Female subjects will be excluded if they have a positive urine pregnancy test, or if they are currently breastfeeding
- 8) Presence of a serious medical illness, including liver, kidney, or cardiovascular disease, or neurological disorder
- 9) Allergy to coconut oil

- 10) Current use of valproate
- 11) Currently enrolled in other research studies or clinical trials involving interventions

Additional Exclusions for MR Component:

- 1) Claustrophobia or metal implanted within the body, body piercings which are not removable
- 2) Cardiac pacemakers, metal clips on blood vessels (also called stents), artificial heart valve, artificial arms, hands, legs, etc., brain stimulator devices, implanted drug pumps, ear implants, eye implants or known metal fragments in eyes,
- 3) Exposure to shrapnel or metal filings (wounded in military combat, sheet metal workers, welders, and others), other metallic surgical hardware in vital area, certain tattoos with metallic ink, certain transdermal (skin) patches such as NicoDerm (nicotine for tobacco dependence), Transderm Scop (scopolamine for motion sickness), or Ortho Evra (birth control), certain intrauterine devices (IUDs) containing metal
- 4) Poor vision, as subjects must have normal or corrected-to normal vision for viewing of cognitive challenge paradigms during fMRI protocols

Concomitant medications will be allowed and will be assessed on a case-by-case basis with the study physician; participants may be excluded if they are taking strong inhibitors or inducers of CYP3A4 (e.g. fluconazole, fluoxetine, fluvoxamine, ticlopidine, St. John's Wort, etc.), CYP2C19 (e.g. ketoconazole, erythromycin, etc.), or CYP2D6 (e.g. paroxetine, bupropion, quinidine, ritonavir, glutethimide, etc.). Dosing schedules may be adjusted in order to offset CBD administration with concomitant medications to decrease the likelihood of any drug-drug interactions. Subjects must have been on stable medication/psychotherapy regimens for at least 3 months prior to starting the study.

Subjects who participate in the open-label phase of the study will not be eligible to also enroll in the double-blind study.

Briefly describe study procedures. Include any local site restrictions, for example, "Subjects enrolled at Partners will not participate in the pharmacokinetic portion of the study." Describe study endpoints.

This study is designed to assess individuals who have expressed interest in using CBD for anxiety. Subjects will complete study visits at McLean Hospital.

A total of 52 (12 in the open-label phase, and 40 in the double-blind phase) female and male participants with anxiety, of minimum age 18, will complete a baseline visit including clinical ratings, an assessment of conventional medication use, quality of life measures, a neuropsychological test battery, a buccal swab sample, and optional neuroimaging (in a subset of participants who are eligible). Participants will subsequently be treated for 6 weeks with the CW sublingual solution. All participants will self-administer 0.5 ml (15 mg of CBD) of solution twice daily (BID). Participants will return to the laboratory or complete remote visits each week to complete clinical ratings and check in with study staff. After 6 weeks of treatment, participants will complete final clinical scales and quality of life measures, a complementary neuropsychological battery, and a corresponding neuroimaging component (where applicable). The open-label phase of the study is expected to take approximately 12 months to complete, and will assess the efficacy of the dose chosen for the double-blind study.

40 female and male participants will be enrolled in the double-blind phase. Study procedures will remain the same as the open-label phase, however participants will receive CW solution or placebo solution in a double-blind, randomized fashion. All participants will self-administer 0.5ml of solution BID for 6 weeks. The double-blind phase of the study is expected to take 24 months to complete.

### **Study Visits**

Subjects will review and sign the approved informed consent form prior to engaging in any study procedures. A structured clinical screening interview (SCID-P or QuickSCID) will be administered, and demographic information, substance abuse/use, and medical histories will also be obtained and reviewed with the study physician. Study inclusion/exclusion criteria will be applied, and appropriate subjects will be enrolled and complete the rest of the study visit.

### **Open-Label Trial**

Subjects will complete study visits at McLean Hospital. Following a preliminary phone screen and prior to any evaluation, all study subjects will be required to sign a McLean Hospital approved informed consent form that describes all study procedures. A structured clinical interview will be administered, and demographic information, substance abuse/use, and medical histories will also be obtained and reviewed with the study physician. Study inclusion/exclusion criteria will be applied, and appropriate subjects will be enrolled and complete the rest of the study visit.

For the first stage of the study, 12 individuals will be assessed at baseline and weekly for 6 weeks of treatment with sublingual CW solution in an open-label fashion: all subjects will receive the CBD product. Subjects will self-administer 0.5 ml (15mg) of CBD sublingually two times daily, in the morning and the evening, for a daily total dose of 30 mg CBD; if no clinical benefit (>15% reduction in BAI ratings) is evident at the 2-week visit, patients will be given the option to add an additional dose in the middle of the day to bring the total daily dose to 45mg CBD. At the weekly visits throughout the treatment period, individuals will complete clinical scales and have a check-in with study staff. In addition to clinical ratings and a check-in with study staff, neuropsychological testing will also be performed at baseline and week 6 in order to assess cognitive performance. A subset of individuals will receive an hour-long MRI scan at baseline and week 6, with both resting state and task-related functional magnetic resonance imaging (fMRI) in each MRI session. In addition, a brief diffusion tensor imaging (DTI) sequence will also be acquired to examine white matter fiber tract integrity, and magnetic resonance spectroscopy (MRS) will be conducted to examine levels of certain metabolites in the brain. Subjects will also provide a buccal swab sample for genetic analysis at the baseline visit; this will allow specification of genes related to degradative enzymes involved in the endocannabinoid system (e.g. FAAH, MAGL) and allow us to determine whether genetic profile can predict treatment response.

At the end of the baseline visit, eligible subjects will receive CBD solution. Subjects will be instructed on how to administer the compound in the morning and evening; they will be instructed how to draw 0.5 dropper of compound, deposit the amount in the dropper under the tongue, hold for 45-60 seconds, then swallow.

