## DATA AND SAFETY MONITORING

Describe the plan for monitoring the data to ensure the safety of subjects. The plan should include a brief description of (1) the safety and/or efficacy data that will be reviewed; (2) the planned frequency of review; and (3) who will be responsible for this review and for determining whether the research should be altered or stopped. Include a brief description of any stopping rules for the study, when appropriate. Depending upon the risk, size and complexity of the study, the investigator, an expert group, an independent Data and Safety Monitoring Board (DSMB) or others might be assigned primary responsibility for this monitoring activity.

NOTE: Regardless of data and safety monitoring plans by the sponsor or others, the principal investigator is ultimately responsible for protecting the rights, safety, and welfare of subjects under his/her care.

Data analyses will be conducted on the open-label phase of the study prior to initiating the double-blind phase in order to ensure that patients derive clinical benefit from the dose selected. Specifically, in conjunction with [REDACTED], we will assess clinical response after the first 5 patients have completed their 6 week trial. If we do not see clinical improvement based on a review of clinical scales, subjective reports and performance, we will consider increasing the dose to 1 droppers two times a day for a total of 60 mg CBD per day. Clinical improvement will be defined as a 15% reduction in BAI scores from baseline. Findings will be used to inform the double blind phase of the study, which would not begin until adequate dose/response is achieved. An amendment would be submitted to the IRB for approval prior to adjusting the dose of CBD.

In the unlikely event that an adverse event occurs, it will be reported to the primary investigator and the Institutional Review Board's guidelines will be followed to ensure adequate reporting and response. All adverse events will be reported to the Partners Healthcare Internal Review Board for their records. There are currently no plans to utilize a Data Safety Monitoring Board (DSMB) due to the extremely low side-effect profile of CBD, but if the IRB deems that an independent DSMB is necessary, the investigators would be happy to suggest individuals who are appropriate or to consider outside suggestions from IRB members.

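### The open-label check of the double-blind dose (30 mg/day) does not separate participants who moved to 45 mg/day at week 2, so improvement at 45 mg/day can count as support for 30 mg/day

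*Combined protocol and SAP*

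**What the plan says.** **Purpose.** Research Design and Methods says of the open-label phase: "This trial will determine whether patients derive clinical benefits at the current dosage proposed for the active treatment arm of the double-blind trial". It adds that this phase "will assess the efficacy of the dose chosen for the double-blind study". Data and Safety Monitoring says that its data are analysed before the double-blind phase starts "in order to ensure that patients derive clinical benefit from the dose selected".

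**Double-blind dose.** For that phase, Research Design and Methods says "All participants will self-administer 0.5ml of solution BID for 6 weeks". At 15 mg per 0.5 ml this is 30 mg/day. No escalation is described for the double-blind phase.

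**Open-label dose.** The Open-Label Trial section starts everyone on 30 mg/day. Participants whose BAI has not fallen by more than 15% at the 2-week visit are "given the option to add an additional dose in the middle of the day to bring the total daily dose to 45mg CBD".

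**The check.** Data and Safety Monitoring says "we will assess clinical response after the first 5 patients have completed their 6 week trial". The judgement is "based on a review of clinical scales, subjective reports and performance", with improvement defined as a 15% fall in BAI from baseline. The double-blind phase waits on an adequate result, and lack of improvement leads to considering 60 mg/day. The section does not mention 45 mg/day. Statistical Approaches compares follow-up with baseline and has no rule for dose received.

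**The concern.** The participants offered 45 mg/day are, by the protocol's own trigger, those who had not met the benchmark on 30 mg/day. They may spend up to 4 of the 6 weeks on 1.5 times the double-blind dose (45/30) before they are assessed. If they then improve, the criterion as written counts that improvement with the rest.

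At stake is the dose check made before 40 people enter the double-blind phase. Its conclusion concerns 30 mg/day, but part of the evidence may come from 45 mg/day. With few participants, one or two who escalate can change the reading. The distortion is largest when 30 mg/day is weak, which is the situation the check is there to detect.

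A related textual problem is that the statements of concentration, amount per dose and daily total do not all agree.

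**Working it through.** **1. The stated doses.** Background and Significance gives about 30 mg/ml.
- 30 mg/ml x 0.5 ml = 15 mg per dose; x 2 = 30 mg/day; x 3 = 45 mg/day. These reproduce the Open-Label Trial figures.
- Research Design and Methods also gives 0.5 ml at 15 mg/ml. Read literally, 15 x 0.5 = 7.5 mg per dose, or 15 mg/day. This conflicts with 30 mg/ml in Background and Significance and with 15 mg per 0.5 ml elsewhere in Research Design and Methods and in Open-Label Trial.
- Research Design and Methods has all participants on 15 mg twice daily, and CBD Administration gives 30 mg/day for the study. Neither allows for the 45 mg/day option.

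**2. Does any rule separate the doses?** Data and Safety Monitoring fixes the time (6 weeks), a number (first 5 completers) and a threshold (15%), but not the dose at assessment. Statistical Approaches does not supply it either.

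**3. How much could it matter?** The plan has no figure to reproduce, so this is an illustration. Assumptions not in the documents:
- BAI mean 22, SD 10, reliability 0.75, modelled as true score plus measurement error, with entry at observed BAI of at least 16;
- a constant effect of 30 mg/day over time;
- escalation if the observed week-2 reduction is 15% or less and the offer is accepted (half or full uptake);
- criterion met if 1 - (cohort mean BAI at week 6 / cohort mean at baseline) is at least 0.15, in cohorts of 5 (100,000 simulated).

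Chance of meeting the criterion:

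| Effect of 30 mg/day | All stay on 30 mg | Pooled, effect proportional to dose (half to full uptake) | Pooled, 45 mg adds 10 points (half uptake) to 20 points (full uptake) |
|---|---|---|---|
| 0% | 0.17 | 0.17 | 0.25-0.60 |
| 10% | 0.46 | 0.51-0.55 | 0.56-0.82 |
| 20% | 0.79 | 0.84-0.88 | 0.84-0.94 |
| 30% | 0.96 | 0.97-0.98 | 0.97-0.99 |
| 50% | 1.00 | 1.00 | 1.00 |

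Proportional means that 45 mg adds half the 30 mg effect, for example 10% becomes 15%. If 45 mg adds nothing, pooled equals all-stay in every row. The share eligible to escalate is 52%, 36%, 22% and 6% at effects of 10%, 20%, 30% and 50%.

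**4. A different reading of the criterion.** Suppose at least 3 of 5 must respond, 40% respond on 30 mg by week 2 and keep that response, all others escalate, and 30% of those respond by week 6. The pooled response rate is 0.4 + 0.6 x 0.3 = 0.58. The binomial chance of 3 or more in 5 is 0.65, against 0.32 if escalators count as non-responders. The 0.32 is a conservative bound, since some might have improved later on 30 mg/day.

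**5. Neither simple substitute is clean.**
- *Stayers only at week 6.* Stayers are selected on response. With a 10% effect and full uptake they meet the criterion with chance 0.68, against 0.46 if all had stayed.
- *Week 2 in everyone.* This is unselected and all on 30 mg/day, but it is a shorter exposure. If the effect is 10% at week 2 and 20% at week 6, week 2 gives 0.46 against 0.79; if it fades from 20% to 10%, week 2 gives 0.79 against 0.46.

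**The case against.** The strongest reply is that this is not a mechanical pass/fail rule. It is an open-label review of several kinds of evidence, by staff who know who escalated and why, and any dose change needs an IRB amendment. A sensible reviewer could separate the doses unprompted. That stands: pooling is possible, not planned. But nothing written asks for the separation, and 15% is the only numerical definition of improvement given.

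Second, the larger figures need a steep dose-response. A rise from 10% to 20-30% for 1.5 times the dose is an assumption. This stands too, which is why the proportional case is shown beside it.

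Third, a reader might infer that 5 patients alone decide whether the double-blind phase starts. The text does not say so. Data and Safety Monitoring opens with analyses of the open-label phase, which may enrol up to 12, and its statement about when the next phase begins is not expressly limited to the first 5. A larger number does not remove the mixing of doses.

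Fourth, Background and Significance reports a 68.29% BAI reduction in 5 completers of a related product. If 30 mg/day of this product did as well, pooling would hardly matter. That is correct, but this phase exists because the benefit of this product at this dose was still to be checked.

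**Conclusion.** The concern holds in a limited form. The open-label phase is described as a check of the double-blind dose, its own escalation option can put week-2 non-responders on a higher dose, and the 6-week criterion does not tell them apart.

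The size is unknown. Under the assumed model with a 10% effect at 30 mg/day, the chance of a favourable reading rises from 0.46 to 0.51-0.55 (proportional effect) or 0.56-0.82 (45 mg adds 10 to 20 points). These ranges are not bounds: the rise is zero if 45 mg adds nothing and close to zero if 30 mg/day works well. They also depend on reading the criterion as a cohort mean in 5 patients.

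Two stronger inferences are not supported. The placebo-controlled comparison is not biased, because its participants are randomised afresh and open-label participants cannot enrol in it; what weakens is the evidence for the dose it uses. Nor do the documents show that 30 mg/day is inadequate or that another dose is preferable.

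The conflicts between the dose statements stand on the text alone and need no model.

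**What to change.** In Data and Safety Monitoring, with a matching sentence in Statistical Approaches:

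- Report BAI by dose received: those who stayed on 30 mg/day and those who moved to 45 mg/day.
- For the 30 mg/day question, show the last BAI before escalation (week 2, when all are on 30 mg/day) next to the week-6 results.
- State that the pooled week-6 result will not be read as evidence for 30 mg/day alone.
- Note beside the table that week 2 is a shorter exposure and that week-6 stayers are selected on response. Week 2 is added to week 6, not substituted for it.

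Separately, reconcile the statements of concentration, amount per dose and daily total in Background and Significance, Research Design and Methods, Open-Label Trial and CBD Administration, including whether the study-wide statements cover the 45 mg/day option. No dose or clinical rule is proposed here.

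The cost is a few sentences and one small table. No new visit is needed: the escalation trigger already requires a week-2 BAI, and Clinical Ratings has anxiety measures at each weekly visit. Daily drug diaries are planned and may document the dose taken, although their content is not described. The downside is that the review may be less conclusive once the doses are separated.
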